APPENDIX 1. STUDY QUESTIONNAIRES (ATTACHED SEPARATELY) [232324](#)

APPENDIX 2. DATA FLOW MAPPING [242425](#)

GLOSSARY OF ABBREVIATIONS

T1D	Type 1 Diabetes
-----	-----------------

KEYWORDS

Diabetes Mellitus, Hyperglycaemia,

STUDY SUMMARY

TITLE	Avoidance of Hyperglycaemia in people with Type 1 Diabetes
DESIGN	Non-interventional, Cross-sectional study
AIMS	To assess how problematic fear of hyperglycaemia is in people with T1D
OUTCOME	Quantitative and qualitative measures
MEASURES	
POPULATION	n=up to 350
ELIGIBILITY	Diagnosis of T1D for at least 6 months
DURATION	1 hour per participant, 9 months total study duration. Participants who participate in the interview study (n=16) will undergo an additional 90 minute interview.

1. INTRODUCTION

1.1 Background

Approximately 400000 people in the UK have T1D (1). Self-management of T1D involves a challenging regimen requiring monitoring of blood glucose levels several times per day and multiple daily insulin injections. People living with T1D can experience a number of psychological difficulties, including feeling burned out, fear of high and low blood glucose levels, adjustment to diabetes-related complications, and problems around eating. Higher levels of diabetes-related distress are associated with a higher HbA1c (2,3) which is associated with increased risk of micro- and macro vascular diabetes-specific complications. The importance of psychological support for people with T1D is increasingly recognised (4), and both published and Imperial data demonstrate the importance of psychological support (5,6).

Published data describe the assessment and consequences of fear of hypoglycaemia in people with T1D (7,8). Hypoglycaemia fear is associated with a higher HbA1c and increased risk of diabetes-related complications. The Hypoglycaemia Fear Survey (HFS-ii) (9,10) is a valid and reliable tool for assessment used in routine clinical care, including in the psychological assessment and intervention outcome data for the Imperial T1D Psychology service. NICE guidelines (11) reference fear of hypoglycaemia as a barrier to achieving HbA1c targets and recommend continuous glucose monitoring for those with extreme fear.

There is, however, little research about fear, or problematic avoidance, of hyperglycaemia in T1D (12). It is, however, a problem that we see in the T1D clinics at Imperial, often with significant adverse consequences. As well as high levels of distress, it is associated with recurrent hypoglycaemia exposure, eroded hypoglycaemia awareness and increased healthcare utilisation (13). More problematically, fear of hyperglycaemia may not be identified, as the HbA1c is often at, or below, target.

1.2 Rationale for current study

Fear of hyperglycaemia represents a gap in knowledge and has implications for clinicians' skills in recognising this problem, and for understanding how best to support the people who experience it.

2. STUDY OBJECTIVES

Primary Objective

Assess how problematic fear of hyperglycaemia is in T1D

Secondary Objectives

Identify whether fear of hyperglycaemia is associated with any clinical factors

Identify the psychological factors that underpin fear of hyperglycaemia

Assess how fear of hyperglycaemia affects self-management of T1D

3. STUDY DESIGN

Non-interventional, cross-sectional questionnaire study in adults with T1D

1 hour per participant, 9 months total

n=up to 350 participants total

Sub study of approximately n=16 participants for semi-structured interviews (1.5 hours per participant)

3.1 Study Outcome Measures

1. Quantitative data:

- a. Hyperglycaemia avoidance scale (HAS)
- b. Hypoglycaemia fear survey (HFS-II)
- c. Problem areas in diabetes scale 5 (PAID-5)
- d. Patient health questionnaire (PHQ-9)
- e. Generalised anxiety disorder scale (GAD-7)
- f. State trait anxiety inventory (Trait subscale)

2. Descriptive data – semi-structured interview

Additional baseline participant data to be pulled from Cerner/via participant survey:

- Age
- Ethnicity
- Length of diabetes
- Current diabetes treatment
- Diabetes complications: nephropathy, neuropathy, retinopathy, cardiovascular disease
- Recent HbA1C
- Other medical conditions
- Other medications
- Hypos – frequency/severity
- Blood glucose monitoring - method and frequency

4. PARTICIPANT ENTRY

4.1 Pre-registration evaluations

Potential participants will be identified by the clinical diabetes team from the list of people who attend the diabetes clinics at Imperial College Healthcare NHS Trust. Participants with type 1 diabetes who do not attend an Imperial College Healthcare NHS Trust diabetes clinic who have consented to be contacted by the Imperial diabetes research team for research purposes will also be invited to participate in the study.

Of the participants who are enrolled in the study, and who have consented to be contacted for an interview, the research team plans to select approximately 16 participants to take part in the qualitative interview. Participants will be selected based on clinician identification and participant self-identification of fear of hyperglycaemia, as well as from a dynamic list of those in the upper quadrant of recorded scores on the Hyperglycaemia Avoidance Scale.

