Of the participants who are enrolled in the study, and who have consented to be contacted for an interview, the research team plans to select approximately 16 participants to take part in the qualitative interview. Participants will be selected based on clinician identification and participant self-identification of fear of hyperglycaemia, as well as from a dynamic list of those in the upper quadrant of recorded scores on the Hyperglycaemia Avoidance Scale.

Participants will be advised that questionnaires should be returned by the end of the study for inclusion in the study analysis.

Within the patient information sheet there will be contact details for the research team, should the participant wish to discuss the study and obtain any further details.

Once returned, the pseudonymised questionnaire data will be recorded in a password encrypted database on an Imperial College Healthcare NHS Trust or Imperial College London computer (subsequently known as the results database). Informed consent will be filed in the trial master file.

Once informed consent has been provided, the research team will then review the electronic health records of those Imperial College Healthcare NHS Trust participants who have consented to record biochemical data, medical history. Other baseline data e.g. demographics will be collected via a participant survey which will be mailed alongside questionnaires. This data will be recorded in pseudonymised form in the results database. Data from Qualtrics will be downloaded in a PDF format on either an ICL or ICHT computer and printed for hard copy records. Questionnaire scoring data will be pulled from Qualtrics in a pseudonymised format and saved on either an ICL or ICHT computer within an encrypted, password protected document.

In all cases, no samples are taken and all data will be pseudonymised. No follow up outside of usual care will be provided.

If participants wish to see their questionnaire scores, they will be able to request this. They will be sent a standardised letter including their scores on each measure and, where available, what this score is suggestive of (e.g. mild depression). Some of the measures do not have standardised cut-offs. This will only be sent if requested and not for all participants.

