Any participant who scores in the severe range on the GAD-7 (scores of 15-21) or the PHQ-9 (scores of 20-27), or who scores 3 on question 9 of the PHQ-9 (this question relates to thoughts of harm to self) will have a letter sent to their GP advising them of this, and the participant will receive a copy.

Any disclosure made to the researchers that constitutes a safeguarding issue, or a potential risk to self or others, will be shared with the clinical team and managed appropriately as per the usual clinical care pathway, including contacting other agencies where indicated. Where participants report mental health problems such as anxiety or depression, based on the Clinical Psychologist's judgement, they will be signposted or, where appropriate, referred, to appropriate mental health services as is usual practice in their clinical care. This might include, for example: their local mental health trust's Single Point of Access; Improving Access to Psychological Therapies (IAPT); the London-wide Type 1 Disordered Eating Service.

If the participant raises concerns that they do not wish to be shared with their clinical care team, but the researcher feels should be shared, an anonymised discussion will be initiated with the Principal Investigator, and if appropriate, the clinical care team. The Trust Ethics Committee can also be consulted, if appropriate, to consider what is in the participant's best interests.

Participants' GPs will not be informed of their participation in the study as it will not affect their care.

End of study will be defined as last subject last visit (LSV).

Sub-study – Qualitative semi-structured interview

Of the participants who are enrolled into the study (and who have consented to be contacted for an interview) the research team plan to select approximately 16 whose HAS scores are relatively higher than other participants in order to conduct a qualitative semi-structured interview. This will be judged from previous research and participants who score in the upper quartile of the entire measure. (Singh *et al.*, 2014). Participants of varying backgrounds will be selected to ensure a mix of demographics, diabetes duration, HbA1c etc. This is in order to ensure a heterogeneous pool of participants to inform our hypothesis.

Participants will not be reconsented to take part in the interview study as they will have already opted in on the original consent form, having read the PIS which details this sub study. The

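### Does letting clinicians nominate interviewees undercut a study of a fear that clinicians may miss?

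*Combined protocol and SAP*

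**What the plan says.** The protocol describes the choice of interviewees four times, in two forms.

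- **Section 4.1 and the earlier part of section 6.** "Participants will be selected based on clinician identification and participant self-identification of fear of hyperglycaemia", followed by "as well as from a dynamic list of those in the upper quadrant of recorded scores on the Hyperglycaemia Avoidance Scale".
- **Sub-study part of section 6, and section 7.** The team will "select approximately 16 whose HAS scores are relatively higher than other participants". The cut is the upper quartile of the scale, and people are chosen to vary in demographics, time since diagnosis and HbA1c. Identification by a clinician or by the participant is not mentioned.

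In all four places the pool is the same: people enrolled in the main study who agreed to be contacted for interview.

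On recognition, section 1.1 says that "fear of hyperglycaemia may not be identified, as the HbA1c is often at, or below, target". It also calls the condition "a problem that we see in the T1D clinics at Imperial, often with significant adverse consequences". Section 1.2 adds that the gap in knowledge "has implications for clinicians' skills in recognising this problem". The objectives in section 2 that the interviews mainly serve are "Identify the psychological factors that underpin fear of hyperglycaemia" and "Assess how fear of hyperglycaemia affects self-management of T1D".

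**The concern.** If clinicians often miss this fear, anyone they nominate is by definition a case they did not miss. They may also notice most readily the people whose fear has already done visible harm. That is an inference from section 1.1, not something it states.

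The 16 places are not divided between routes, the clinician route has no upper limit, and no place is kept for a high scorer whom clinicians have not recognised. Clinician recognition is not among the characteristics to be varied, nor in the baseline data listed in section 3.1.

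At stake is the range of the interview themes. They could lean towards recognised cases and say less about people with unremarkable HbA1c, whom section 1 suggests clinicians find hardest to spot. Because section 7 justifies 16 by saturation, a thin supply of such people could make saturation appear to be reached too early.

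**Working it through.** **No figure to reproduce.** The 16 in section 7 is a saturation judgement with no numerical inputs. The check is a comparison of the two rules, then an illustration.

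**The rules side by side**

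| | Section 4.1 and early section 6 | Sub-study text of section 6, and section 7 |
|---|---|---|
| Clinician identification | a route | not used |
| Self-identification | a route | not used |
| High HAS score | a route | the rule |
| Spread of backgrounds, including HbA1c | not stated | stated |
| Open to a high scorer unknown to clinicians | yes, by the HAS list | yes |

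The rules differ on whether an identified person below the HAS cut can be interviewed. Neither shuts out an unrecognised high scorer, if the HAS list is read as a further source, which is the natural reading of "as well as from a dynamic list of those in the upper quadrant of recorded scores on the Hyperglycaemia Avoidance Scale". If it were read as one of several joint conditions, such people would be excluded. The second rule, which has no clinician condition, tells against that reading.

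**Size of the HAS list.** The upper quartile is N/4, before interview consent is applied. From the maximum of 350 participants it is 350/4 = 87.5. From 200, 100 and 64 it is 50, 25 and 16. The list will usually exceed 16, so there is room to choose from it.

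**Expected unrecognised interviewees.** Let k be the places filled by clinician identification and r the share of high scorers whom clinicians already recognise. Both are assumed, because the documents give neither. With the other places drawn at random from the HAS list, the expected number is (16 − k)(1 − r).

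| k | r = 0.1 | r = 0.3 | r = 0.5 |
|---|---|---|---|
| 0 (HAS-only rule) | 14.4 | 11.2 | 8.0 |
| 4 | 10.8 | 8.4 | 6.0 |
| 8 | 7.2 | 5.6 | 4.0 |
| 12 | 3.6 | 2.8 | 2.0 |

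At r = 0.5 the binomial chance of fewer than 4 unrecognised interviewees is 1% for k = 0, 7% for k = 4, 36% for k = 8 and 94% for k = 12. The number is small only when clinicians fill about half the places or more, or already recognise most high scorers.

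**Would reserved places help?** Suppose at least 8 of the 16 were kept for unrecognised high scorers and most of the rest went to recognised ones.

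- Against the HAS-only rule, the floor of 8 lies below the expected 14.4 (r = 0.1) and 11.2 (r = 0.3), and equals the 8.0 at r = 0.5.
- Take a theme held by 20% of unrecognised people and by no recognised people (assumed, and an extreme case). The chance of hearing it at least once among n unrecognised interviewees is 1 − 0.8^n: 91% for n = 11, 83% for n = 8 and 59% for n = 4. The chance of hearing it in two or more interviews is 68%, 50% and 18%.
- Moving from 11 to 8 would therefore lose ground. The floor gains only where the clinician route is used heavily, for example 8 against 5.6 or 4.0 at k = 8.

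**The case for a change.** The best case for a change is that the text permits any value of k, including values at which few unrecognised people are heard. The spread of HbA1c appears in only one of the two rules, and HbA1c is not the same thing as recognition. If recognition is never recorded, its influence on the themes cannot be examined later. A clinician field and a survey item would be cheap.

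Part of this stands. The presence of unrecognised interviewees is likely but not guaranteed, and the two rules do not match. Four points keep it from requiring a change.

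- Self-identification and participants from outside Imperial clinics also bring in people whom local clinicians have not flagged. Varying HbA1c addresses the reason section 1.1 itself gives for missed cases.
- Clinician nomination has a use. The HAS measures avoidance, so a fearful person may score below the cut. For interviews about the experience of fear, including people known to have it is ordinary purposive sampling.
- Section 6 describes an inductive approach in which each round of analysis shapes the interviews that follow. Fixed quotas set beforehand fit poorly with that, and reporting by recognition group would impose a comparison that section 2 does not ask for.
- Recognition status is harder to collect cleanly than it looks. Asking clinicians only about high scorers reveals that those people scored high. Keeping clinicians unaware of the score means asking about every clinic attendee who opted in, and there may be no answer for people who attend elsewhere.

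**Conclusion.** No change to the plan is called for. The tension between section 1.1 and the clinician route is real, but it shows only that hearing from unrecognised people is not guaranteed. They remain eligible under both rules, and under the HAS-only rule they would be an expected 8.0 to 14.4 of 16 if clinicians recognise 50% to 10% of high scorers. With half the places filled by clinicians, the figure is 4.0 to 7.2. Those ranges rest on assumed recognition rates, an assumed split of places and random choice from the HAS list, so they show how the numbers behave and do not estimate a bias.

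Fixed reservation of places is not a clear gain. It helps only if the clinician route is used heavily, can fall below what the HAS-only rule already delivers, and sits awkwardly with grounded-theory sampling. What is left is missing detail and a clerical slip: two wordings of the selection rule, with *quadrant* in two places where *quartile* is evidently meant. The team can settle this in conduct and describe how interviewees were found when reporting the themes. The sub-study is exploratory, and no questionnaire result depends on it.

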4.2 Inclusion Criteria

- Previous diagnosis of Diabetes Mellitus of at least 6 months
- Aged 18 or above

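### The first inclusion criterion in Section 4.2 asks only for diabetes mellitus, while the Study Summary, primary objective and design line confine the study to type 1 diabetes

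*Combined protocol and SAP*

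**What the plan says.** Section 4.2 has two inclusion criteria. One is age 18 or above; the other is "Previous diagnosis of Diabetes Mellitus of at least 6 months". The three exclusion criteria concern English language, inability to take part for other reasons as judged by the Chief Investigators, and pregnancy. None refers to type of diabetes.

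Elsewhere the population is type 1 diabetes. The Study Summary gives eligibility as "Diagnosis of T1D for at least 6 months", the title as "Avoidance of Hyperglycaemia in people with Type 1 Diabetes" and the aim as "To assess how problematic fear of hyperglycaemia is in people with T1D". The primary objective in Section 2 is "Assess how problematic fear of hyperglycaemia is in T1D". Section 3 describes a "Non-interventional, cross-sectional questionnaire study in adults with T1D".

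Sections 4.1 and 6 describe two recruitment sources: people attending the Trust's diabetes clinics, and people from outside the Trust who have agreed to be contacted for research. Section 4.1 states type 1 diabetes for the second source only. Section 7 says that about 350 people have been identified, without giving their type.

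**The concern.** The protocol contains two eligibility statements with the same minimum duration and different diseases, and the wider one stands in the criteria list. Anyone who meets the Summary on disease type also meets Section 4.2, but the reverse is not true.

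What is at stake is the match between those who may be enrolled and those the conclusions describe. Scores from a person without T1D would enter the HAS results for an objective stated for T1D. They would also enter the ranking of high HAS scorers, which is one route to the approximately 16 interviews, alongside clinician and self-identification. Section 7 plans no restriction or subgroup by type that would separate such scores. An audit against Section 4.2 (audits are foreseen in Section 8.7) would have no written criterion by which to call the entry an error.

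**Working it through.** No arithmetic applies beyond counting, so the check sets the statements side by side.

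| Place | Wording | Type specified? |
|---|---|---|
| Study Summary, title | "Avoidance of Hyperglycaemia in people with Type 1 Diabetes" | Yes |
| Study Summary, aims | "To assess how problematic fear of hyperglycaemia is in people with T1D" | Yes |
| Study Summary, eligibility | "Diagnosis of T1D for at least 6 months" | Yes |
| Section 2, primary objective | "Assess how problematic fear of hyperglycaemia is in T1D" | Yes |
| Section 3, design | "Non-interventional, cross-sectional questionnaire study in adults with T1D" | Yes |
| Section 4.2, first inclusion criterion | "Previous diagnosis of Diabetes Mellitus of at least 6 months" | No |

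The count is 3 (Summary) + 1 (objective) + 1 (design) = 5 statements that specify T1D, against 1 that does not. The third secondary objective also refers to T1D, which would make it 6 to 1.

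Next, could other text supply the missing restriction?

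1. **Second inclusion criterion.** It sets age only.
2. **Exclusion criteria.** None of the three names type. The Chief Investigators' discretion is about being unable to participate, not about the kind of diabetes.
3. **Recruitment source.** Of the 2 sources, 1 is explicitly limited to type 1. For the other, Section 6 starts from a database covering everyone who attends the Trust's diabetes clinics. Section 1.1 mentions "a problem that we see in the T1D clinics at Imperial", but that is background and not a selection rule.
4. **The Summary as the screening list.** Its eligibility row has neither the age limit nor the exclusions, so it cannot stand in for Section 4.2.
5. **Detection after enrolment.** Section 3.1 lists "Current diabetes treatment", and Section 6 plans a record review for consenting Trust participants. Either could reveal type. The survey and questionnaires are not reproduced and may ask about it. The text available describes no explicit check of type and does not say how scores are handled if a participant proves not to have T1D.

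None of these restores the restriction in writing. The part of the sample that could be affected is the Trust-clinic share of the approximately 350, which is not stated.

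**The case against.** The strongest reply is that this is a drafting slip with no practical effect. The Summary row is itself an eligibility statement. Section 6 has the clinical team pick eligible people from the database without citing a section, so the term can be read as pointing to that row. The protocol uses the general disease term loosely elsewhere, in the keywords and in the adverse event section. Section 4.1 says that people with type 1 diabetes from outside the Trust will also be invited, which suggests that the Trust group was meant to have type 1 too. The people already identified may all have T1D.

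Most of this stands as evidence of intent. It supports treating the wider wording as an error and not as a second target population. It also limits what can be claimed: that eligibility in Section 6 refers to Section 4.2 is the natural reading but an inference, and the lack of a visible type check is weak evidence when the survey is not shown. The withdrawal rule in Section 4.3, under which data already collected are kept, does not address people found ineligible and is not relied on here.

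Clear intent does not make the criterion correct, however. Section 4.2 is the only full list of entry criteria, and as written it describes a different population.

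**Conclusion.** The inconsistency is real and follows from the text alone. Section 4.2 is wider than the population in the title, aim, Summary eligibility row, primary objective and design line, and nothing else in the documents narrows it for Trust clinic attenders. It should be fixed, because it is a wrong rule in operative text and not merely loose background wording.

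Confidence is high for the mismatch only. The documents do not show that anyone without T1D has been or is likely to be enrolled. The size of any bias cannot be determined without the number of clinic attenders who do not have T1D and HAS scores by type. The conclusion assumes that the five T1D statements express the intended population, which the whole protocol supports.

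**What to change.** Reconcile Section 4.2 with the Study Summary: in the first inclusion bullet, replace the general disease term with type 1 diabetes and keep the minimum of 6 months. The reference to eligible people in Section 6 then restricts both recruitment sources with no further edit. The cost is one line, handled as a small amendment to documents that already have ethics approval (Section 8.1).

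An optional safeguard is to confirm type before analysis, using the record review planned for Trust participants and the participant survey, and to report anyone found not to have T1D separately from the T1D results. No new data item is needed if the survey, treatment or medical history already shows type. If the survey does not ask, non-Trust participants would need one added question in both the online and paper versions.
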